8.2.1 OUTCOME MEASURES IN AML

Outcome	Definition	Response Category	Point of Measurement
Overall survival	Defined for all patients of a trial; measured from the date of entry into a study to the date of death from any cause; patients not known to have died at last follow-up are censored on the date they were last known to be alive.	All patients	Trial entry
Event-free survival	Defined for all patients of a trial; measured from the date of entry into a study to the date of relapse from PR or CR or CRI, or death from any cause; patients not known to have any of these events are censored on the date they were last examined.	All patients	Trial entry

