3.2.2 SECONDARY ENDPOINT(S)

Endpoint	Start	End
1. Overall incidence of treatment-related and non-treatment related toxicity..		30 days after last dose of study agent
2. Duration of response. For patients that achieve \geq PR, how long do they maintain this response before progression.	First dose of JNJ-40346527	
3. Event-free survival at 12-months		12 months from first dose
4. Overall survival at 12-months		Death (or date of last contact)

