4.5 PARTICIPANT SCREENING AND ENROLLMENT

In order to participate in this study, signed informed consent must be obtained from the participant or the participant's legally acceptable representative. The current Institutional Review Board (IRB) approved informed consent must be signed and dated by each participant prior to undergoing any study procedures or before any prohibited medications are withheld from the participant in order to participate in this study.

This study consists of a 28 day screening period. Screening will begin once the participant has provided written informed consent to participate in the study and ends on Day 0 of the study. All screening and baseline evaluations will be performed during the screening phase. Eligible participant assignment to one of two treatment arms, *assay positive* or *assay negative*, based on results from *ex vivo* screening assay will occur no later than 14 days prior to starting treatment with study agent. Samples will be collected from study eligible participants no later than 14 days prior to initiating treatment with study agent. Day 1 of the clinical trial will be when participants are started on JNJ-40346527. Total accrual of all participants is anticipated to take a total of 24 months.

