4.7.1 SCREEN FAILURE

Any participant that has signed the consent form (for either screening or study participation) but does not meet the study eligibility criteria, or meets study eligibility criteria but terminates the participation prior to receiving study treatment, will be considered a screen failure. The reason for screen failure should be captured in the database for each participant failing to meet the eligibility criteria.

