7.4.1 INFORMATION TO BE COLLECTED ON SCREENING FAILURES

A participant who signed an informed consent form but failed to be started on treatment for any reason will be considered a screen failure. Those found not to be eligible after signing the main study consent will be considered screening failures, and data will be handled in the same manner. The demographic information and informed consent. No other data will be entered into the clinical database for individuals who are screen failures.

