10.1 ANALYSIS POPULATIONS

Most common analysis populations are described below:

Analysis Population	Definition	Endpoint
Intent to Treat (ITT)	Those who consent and are registered for the trial regardless of actual receipt of screening or treatment	Used to report accrual
Evaluable for Safety	Those who received at least one dose of JNJ 40346527	Incidence of DLT and SAE
Evaluable for Response	Those who received at least one cycle of JNJ 40346527 and have response measurements	Best objective response
Evaluable for Overall Survival and Event-Free Survival	Those who received at least one dose of JNJ 40346527 and have survival information	Overall survival

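### Section 8.2.1 counts OS and EFS from an undefined study entry date, but section 3.2.2 ends EFS 12 months from first dose and section 10.1 analyses only dosed patients, so any entry date before dosing adds guaranteed event-free time

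*Combined protocol and SAP*

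**What the plan says.** **Time origin.** Section 8.2.1 defines OS as "measured from the date of entry into a study to the date of death from any cause" and EFS as "measured from the date of entry into a study to the date of relapse from PR or CR or CRI, or death from any cause". Its point-of-measurement column gives trial entry for both, and both are said to cover all patients.

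Section 3.2.2 ends EFS at "12 months from first dose". Its Start column reads "First dose of JNJ-40346527". In the available text that entry is printed once, on the duration-of-response row, and the Start cells for toxicity, EFS and OS are blank.

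**Who is analysed.** Section 10.1 defines the OS and EFS set as "Those who received at least one dose of JNJ 40346527 and have survival information". Section 4.7.1 says that an eligible patient who "terminates the participation prior to receiving study treatment, will be considered a screen failure". Section 7.4.1 says: "A participant who signed an informed consent form but failed to be started on treatment for any reason will be considered a screen failure". It adds that only demographic and consent information is kept for such patients.

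**Time between joining and dosing.** Section 4.5 sets a 28-day screening period that begins at consent. It also states: "Samples will be collected from study eligible participants no later than 14 days prior to initiating treatment with study agent". Arm assignment carries the same 14-day limit. Section 7.4 requires the assay to be complete at least 7 days before treatment. Section 3.1 allows rescreening.

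**The concern.** A time-to-event endpoint needs one origin, and the analysed patients should be at risk of an observable event from that origin. Here the origin may lie before first dose, while membership of the analysis set is decided at first dose. A patient who dies in between becomes a screen failure and leaves the analysis. A patient who stays in has, by construction, survived the interval. EFS is affected in the same way, because its events are death and relapse from a response, and an analysed patient can have neither before treatment starts.

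12-month EFS and 12-month OS are listed secondary objectives (section 2.2). The trial is not randomised, so these rates will be read mainly against outside figures, and such a comparison depends on where the clock starts. The two sections can also classify one patient differently. With a 28-day gap, a patient who dies 351 days after first dose dies 351 + 28 = 379 days after entry. That patient has had an event by 12 months from first dose but is event-free at 12 months from entry.

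**Working it through.** **1. The plan's own figures.** The documents give no target rate, event count or power for OS or EFS, so there is no survival figure to reproduce. The one design figure is the 80% power of the Simon rule (continue with at least 1 response in 7; promising with at least 3 in 14; 5% against 30%). The exact calculation is the sum over x = 1 to 7 of P(X1 = x) × P(X2 ≥ max(0, 3 − x)), with X1 and X2 each binomial on 7 patients. It gives 0.810 at a rate of 30% and 0.027 at 5%. The stated design reproduces, and nothing below alters it.

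**2. Is there a conflict?**

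| Item | 8.2.1 | 3.2.2 | 10.1 |
|---|---|---|---|
| EFS clock | study entry | ends 12 months from first dose | not stated |
| OS clock | study entry | first dose, if the Start cell is merged | not stated |
| Patients | all in the trial | not stated | dosed only |

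Section 10.2.2 names Kaplan-Meier and cumulative incidence curves but no origin, so it does not settle the matter.

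**3. Direction.** Let g be the time from entry to first dose. In a dosed-only set no event can fall within g, so

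S_entry(12 months) = S_dose(12 months − g) ≥ S_dose(12 months).

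This holds for any hazard. Equality for every hazard requires g = 0.

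**4. Range of g.** Entry is undated, so g is an assumption. The values used are 7 days (the assay limit in 7.4), 14 days (the assignment limit in 4.5 as written) and 28 days (the full screening period, if entry is consent). A smaller gap is possible, down to zero if entry is Day 1. Keeping a first consent date after rescreening would make it longer.

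**5. Size for OS.** Constant hazard h is assumed, with 30.44 days per month: S = exp(−h × (12 − g/30.44)).

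- *Section 1.1 ceiling of 10% 3-year OS:* h = −ln(0.10)/36 = 0.0640 per month, a median of 10.8 months.
- *Median of 4 months (assumed; not in the documents):* h = ln(2)/4 = 0.1733 per month.

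| Gap g | 12-month OS, 10% at 3 years | 12-month OS, 4-month median |
|---|---|---|
| 0 (first dose) | 46.4% | 12.5% |
| 7 days | 47.1% | 13.0% |
| 14 days | 47.8% | 13.5% |
| 28 days | 49.2% | 14.7% |

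In the second column the relative increase exp(h × g/30.44) − 1 is 8% at 14 days and 17% at 28 days. Over medians of 3 to 10.8 months and gaps of 7 to 28 days, the 12-month rate rises by 0.3 to 2.9 percentage points. The median rises by g itself, 0.23 to 0.92 months. EFS shifts by the same rule, but the documents give no EFS rate from which to size it.

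**6. Scale.** With 14 patients in an arm, one patient is 1/14 = 7.1 points. The shifts in the first column, 0.7 to 2.8 points, equal about 0.1 to 0.4 of a patient per arm.

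**The case against.** The strongest reply is that entry may simply mean Day 1. Section 4.5 calls the day of first dosing Day 1 of the clinical trial. Section 7.3.2 places the ex vivo assay before entry, which argues against consent at the start of screening. Section 3.1 says that screen failures are not included in the study, so all patients of the trial could mean the treated ones. On that reading the gap is zero and the sections agree. This much stands: a reader might infer that the plan builds in a proven 14 to 28 days of immortal time, and the documents do not support that. They never date entry, and 7.4 allows a gap of 7 days or possibly less. They do not equate entry with Day 1 either. Section 10.1 describes people registered for the trial whether or not they are treated, and registration and arm assignment precede dosing.

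A reader might also infer that 3.2.2 contradicts 8.2.1 outright for both endpoints. Only EFS is explicit. A merged Start cell is the natural reading of a table with one printed entry and blank neighbours, but for OS it remains an inference from text extracted from a PDF.

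Finally, the effect is small against the noise. At 46.4% with 14 patients, a rough 95% interval is ±1.96 × √(0.464 × 0.536/14), about 26 points. OS and EFS carry no test or threshold, and both arms would use the same clock. All of this is correct, and it limits the importance of the point. It does not remove the contradiction, and a shift that can only go upward is not of the same kind as sampling error.

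**Conclusion.** The point holds in a conditional form. The EFS origin is contradictory between 8.2.1 and 3.2.2. The OS origin is probably so. The population in 8.2.1 does not match 10.1. Whether reported survival would be inflated depends on what entry means: any date before first dose raises both 12-month rates, and Day 1 leaves them unchanged.

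Under the section 1.1 ceiling and constant hazard, the increase in 12-month OS is 0.7 points at 7 days, 1.4 at 14 and 2.8 at 28. With an assumed 4-month median it is 1.0 to 2.2 points at 14 to 28 days. The larger relative figures (8% to 17%) come from dividing by a small rate under a median the documents do not give. The effect is modest and confined to descriptive secondary endpoints. It does not bear on the primary endpoint, the futility rule or the safety boundary. It is worth correcting because the edit is nearly free and should be made before anyone can choose the origin with results in hand.

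**What to change.** - In 8.2.1, for both OS and EFS, replace the study-entry wording and the trial-entry label with the date of first dose of JNJ-40346527.
- In the same table, replace the reference to all patients with the dosed set of 10.1.
- In 3.2.2, write the first-dose start explicitly in the EFS and OS rows.

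This is a wording change to two tables, with no new data and no operational burden. If entry was meant to precede dosing, the reported 12-month figures become slightly less favourable. If it meant Day 1, they do not change.

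Keeping entry as the origin would be coherent only if its date were defined and every entered patient were analysed. That would require survival data on undosed patients, which 7.4.1 does not now collect, so it is the costlier route.

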We anticipate that *ex vivo* sensitivity will predict participants’ response and that only the assay positive arm will continue to enroll in stage 2. The expected total enrollment of both Arms would be 21 participants in this case. If no participant responds in either treatment arm, the enrollment will end with 14 patients. If ≥ 1 out of 7 eligible participants respond to JNJ-40346527 in both the assay positive and assay negative arms, then both arms will continue to stage 2. In this case, the maximum enrollment would be 28 participants.

This study has a stopping rule for both futility (a lack of efficacy) and safety. No response among the first 7 patients is defined as futility and will halt each either arm of the study.

Likewise, excess toxicity will suspend enrollment if the lower 90% confidence interval for Grade 3 or higher treatment-related toxicity exceeds 30% (considered acceptable dose-limiting toxicity (DLT) incidence).

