8.2 RESPONSE CRITERIA FOR AML

The objective response rate will be defined as \geq PR, including cytogenetic and molecular responses when applicable, and will be determined at the end of each cycle.

Complete Remission (CR)*:

- Bone marrow blasts < 5%;
- Absence of blasts with Auer rods;
- Absence of extramedullary disease;
- Absolute neutrophil count $>1 \times 10^9/L$ (1000/ μ L);
- Platelet count $> 100 \times 10^9/L$ (100,000/ μ L);
- Independence of red cell transfusions

Morphologic CR:

- Bone marrow blasts <5%;
- Absence of blasts with Auer rods;
- Absence of extramedullary disease;
- No hematologic recovery required

Partial Remission

- Relevant in the setting of phase 1 and 2 clinical trials only;
- All hematologic criteria of CR;
- Decrease of bone marrow blast percentage to 5% to 25%;
- Decrease of pretreatment bone marrow blast percentage by at least 50%

Cytogenetic Complete Remission (CRc):

- Reversion to a normal karyotype at the time of morphologic CR in cases with an abnormal karyotype at the time of diagnosis; based on the evaluation of 20 metaphase cells from bone marrow.

Molecular CR (CRm):

- Molecular studies are negative (i.e., normal molecular markers in persons with previously abnormal molecular studies (e.g. c-KIT, NPM1, FLT3).

CR with incomplete recovery (CRI): • All CR criteria except for residual neutropenia ($< 1 \times 10^9/L$ [$1000/\mu L$]), or thrombocytopenia ($< 100 \times 10^9/L$ [$100,000/\mu L$]).

Stable disease (SD) Not fulfilling either PR or PD criteria and clinical stability

Progressive disease (PD) Increase in blasts by $\geq 50\%$

Definitions of response criteria are amended from Cheson et al.²⁰

*All criteria need to be fulfilled; marrow evaluation should be based on a count of 200 nucleated cells in an aspirate with spicules; if ambiguous, consider repeat exam after 5 to 7 days; flow cytometric evaluation may help to distinguish between persistent leukemia and regenerating normal marrow; a marrow biopsy should be performed in cases of dry tap, or if no spicules are obtained; no minimum duration of response required.

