10.2 DESCRIPTION OF STATISTICAL METHODS

10.2.1 ANALYSIS OF PRIMARY ENDPOINT(S)

A Simon 2-stage minimax design will be used to determine best objective response. For each arm, we will enroll 7 patients in the first stage. If there is at least 1 response among the first 7 patients, we will proceed to the second stage and enroll an additional 7 patients. The treatment is considered promising if we have at least 3 responses among 14 patients. We will estimate the best objective response and exact confidence interval using the binomial distribution for each arm separately.

Response assessment will be based on best objective response rates within the first 2 cycles of study drug, including CR, CR with inadequate bone marrow recovery, partial response, stable disease, or progressive disease as defined by Cheson et al.²⁰

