10.2.2 ANALYSIS OF THE SECONDARY ENDPOINT(S)

For the secondary endpoints, we will estimate the incidence of the overall incidence of treatment-related and non-treatment related toxicity and the exact confidence interval. In addition, each toxicity event will be tabulated and summarized by severity and major organ site according to the CTCAE v5.0. Time-to-event analysis (e.g., Kaplan-Meier and cumulative incidence curves) will be used to evaluate event-free and overall survival.

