10.3 SAMPLE SIZE, POWER, ACCRUAL RATE AND STUDY DURATION

10.3.1 SAMPLE SIZE AND POWER

The sample size for each group was derived according to the 2-stage design with minimax criteria using the following parameter settings: 1) 80% power; 2) 5% significance level; 3) historical response rate of 5% (poor response), and 4) desired response rate of 30% (promising response).²¹ The sample size and power analyses were conducted using PASS 14 software (<http://www.ncss.com/software/pass/>). Based on the expected accrual rate of 14 participants per year, we anticipate this trial to take 36 months (24 months of accrual and 12 month of minimum follow-up).

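### Event-free survival counts no progression in participants who never respond, so in non-responders its only event is death, as in overall survival

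*Combined protocol and SAP*

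**What the plan says.** Section 8.2.1 defines two outcomes for all patients, both measured from trial entry. OS ends at death, with censoring at the date last known alive. EFS runs "to the date of relapse from PR or CR or CRI, or death from any cause"; otherwise "patients not known to have any of these events are censored on the date they were last examined".

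Section 8.2 has a PD category that needs no earlier response: "Progressive disease (PD) Increase in blasts by" at least 50%. It does not say in which sample, against which reference value, or whether the 50% is relative or in percentage points.

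Sections 2.2 and 3.2.2 list EFS at 12 months as a secondary endpoint. Section 10.1 puts EFS and OS in the set with at least one dose and survival information. Section 10.2.2 says that time-to-event methods, such as Kaplan-Meier and cumulative incidence curves, "will be used to evaluate event-free and overall survival". None of these sections lists events.

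**The concern.** A reader of a 12-month EFS figure will normally assume that leukaemia progressing on treatment counts as failure. Under the written definition it counts only after a response. A participant whose blasts rise from the start stays event-free until death, or is censored at the last examination.

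Most participants in this design may be non-responders. The synopsis lists EFS among the efficacy assessments to be looked at by ex vivo sensitivity, and Section 3.1 anticipates that "only the assay positive arm will continue to enroll in stage 2". In an arm that stops for lack of response, the EFS curve would consist of deaths, apart from any late responder who relapses, and would largely restate OS. What is at stake is the meaning of a secondary endpoint, not the go/no-go decision.

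**Working it through.** **1. Event sets side by side (Section 8.2.1).**

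| Participant | EFS events | OS event |
|---|---|---|
| Responder (PR, CR or CRi) | relapse, death | death |
| Non-responder who meets PD | death | death |
| Non-responder with stable disease | death | death |

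In the last two rows the event sets are identical. Only censoring differs: last examined for EFS, last known alive for OS.

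**2. Does another section supply the missing event?** Sections 2.2, 3.2.2, 10.1 and 10.2.2 name or analyse EFS and add no event. Section 8.2 defines PD but does not link it to EFS. A footnote to the schedule in Section 7.10 ends treatment at progression by the working-group criteria, again without a link. Section 6.3 defines progression only as loss of an earlier response of at least PR. The gap stays open.

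**3. How many participants does it touch?** The inputs are the test rates of 5% and 30% (Section 10.3.1), 7 participants in stage 1 with at least 1 response needed to continue, and the final rule: "The treatment is considered promising if we have at least 3 responses among 14 patients".

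The plan's own figure comes first. Power = P(at least 3 of 14) − P(0 of 7) × P(at least 3 of the next 7).
- At 30%: 0.839 − 0.082 × 0.353 = 0.810, which agrees with the stated 80%.
- At 5%: 0.0301 − 0.698 × 0.0038 = 0.0274, within the 5% limit.

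Non-responder counts on the same inputs:
- Share at the test rates: 1 − 0.30 = 70% and 1 − 0.05 = 95%.
- Arm stopped at 0 of 7: all 7, barring later responses. Probability 0.95^7 = 0.698 at a 5% rate and 0.70^7 = 0.082 at 30%.
- Arm at the 3-of-14 boundary: 11/14 = 79%.
- One arm stopped at 0 of 7 and the other at 3 of 14. Section 3.1 says of the one-arm path: "The expected total enrollment of both Arms would be 21 participants in this case". Then (7 + 11)/21 = 86%.

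These are counts of response-evaluable participants. The EFS set needs only one dose, and Section 4.6.1 allows some early discontinuations to be replaced, so it may be larger.

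**4. Can the effect on 12-month EFS be sized?** Not from the documents, which give no survival figure for non-responders in this trial. Suppose progressed survivors go on being examined and non-responder survival is exponential with median m months. The written EFS then exceeds one that counts PD by about w × (1 − s) × 2^(−12/m), where w is the non-responder share and s the share with lasting stable disease. All of the following are assumptions:
- w = 0.70, s = 0.5, m = 3: 0.70 × 0.5 × 0.0625 = 2.2 points.
- w = 0.95, s = 0, m = 6: 0.95 × 0.25 = 23.8 points.
- w = 0.95, s = 0, m = 9: 0.95 × 0.397 = 38 points.

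The answer follows the assumed m. If instead progressed survivors are censored when PD is found and data are cut at 12 months, survivors leave the risk set early while the deaths stay in, so the written curve falls too. Simulation of that case gave a difference of 0.0 to 4.1 points. It assumed w of 0.70 or 0.95, m of 3 to 6, s of 0 to 0.5, PD at day 28 to 84, and a responder EFS median of 3 to 12 months. One participant in an arm of 14 is 1/14 = 7.1 points.

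**5. Would adding PD be enough?** Not as Section 8.2 stands. If PD is judged on marrow blast percentage, a relative rise of 50% is impossible above a baseline of 100/1.5 = 66.7%, and a rise of 50 percentage points is impossible above 50%. If another sample or measure is meant, these ceilings do not apply. The text does not say which is intended.

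**The case against.** The strongest case on the other side has four parts.

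First, EFS is secondary, descriptive and unpowered, and neither the futility rule nor the 3-of-14 rule uses it. This stands and limits the weight of the point.

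Second, disease status in non-responders is not lost, because Section 10.2.1 classifies best response down to stable and progressive disease. This is true, but a category has no date and does not enter the EFS curve.

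Third, a reader might infer that EFS as planned does not measure disease control at all. The documents do not support that, since relapse in responders is an event. A reader might also take 70% to 95% as the expected share of non-responders. The rates of 5% and 30% are the poor and desirable values of the test, not forecasts, and the counts out of 7, 14 and 21 are Simon counts, not the EFS population.

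Fourth, a reader might infer that 12-month EFS is inflated by a known amount, perhaps 20 points or more. That rests on a survival median from outside the documents and on progressed survivors still being examined. Under the censoring rule in Section 8.2.1 with a 12-month cut, the difference may be close to zero.

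None of this supplies the missing event.

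**Conclusion.** The point holds in a limited form. As written, a participant who progresses without ever responding has no EFS event before death, so in non-responders EFS repeats the OS event and says nothing about disease control. This follows from the wording of Section 8.2.1 and needs no assumption. Its reach depends on the response rate and could cover most of an arm, but late responses would lower the counts and the one-dose EFS set may be larger than them. The direction is generally towards a more favourable EFS; the amount at 12 months cannot be stated from the documents. The definition should be corrected before EFS is analysed. The primary analysis, the sample size and the Simon decision are unaffected.

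**What to change.** - In Section 8.2.1, define EFS as time to the earliest of: PD per Section 8.2 in a participant without prior response; relapse or loss of any response counted under Section 8.2; or death from any cause. State whether morphologic CR is a counted response. Section 8.2 lists it, but the present EFS definition does not name it, so its loss could otherwise remain without an event.
- In Section 8.2, give the sample, the reference value and the scale for the 50% blast increase.
- Add a sensitivity analysis that also counts, as an event at last dose, non-responders whose recorded reason for stopping is disease progression but who have no marrow documenting PD. Section 4.6 already lists progression among the reasons for stopping.
- The sponsor must reconcile the differing uses of progression in Sections 6.3, 7.10 and 8.2, because the recorded reason for stopping depends on them. No treatment-stopping rule is proposed here.

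The cost is a change of definition and one extra analysis. Section 7.2.5 already schedules marrows at Day 29 of cycles 1 to 3 and every 3 months afterwards, so no visit is added. EFS will become less favourable. It must be confirmed that the case report form captures a PD date for non-responders. Some progression after treatment stops may still go undated, since Section 7.7 sets follow-up at 6-month intervals and Section 7.10 allows contact by phone.

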7.6 END OF TREATMENT VISIT

Participants will be followed until death. Participants will be evaluated for end of treatment within \pm 7 days after stopping JNJ-40346527. End of treatment assessments are listed in the Section 7.10, Schedule of Events . If participants do not reach the end of treatment due to transition to hospice or death, an end of treatment visit will not be conducted.

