7.7 FOLLOW-UP

Participants will be followed every 6 months until death. Participants removed from protocol therapy for unacceptable AE(s) will be followed until resolution or stabilization of the AE.

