7.10 SCHEDULE OF EVENTS

Ex vivo screening	X		X	X		X			
FACS	X			X		X			
RNAseq	X	X		X		X			
Research Blood Samples ^K	X	X	X	X	X	X	X	X	

* In general, assessments/procedures are to be performed on Day 1 and prior to the first dose of treatment for each cycle unless otherwise specified. Treatment cycles are 28 days; however the treatment cycle interval may be increased due to toxicity according to the dose modification guidelines provided in Section 6.2.. If the interval is increased, all procedures except imaging should be performed based on the new dosing schedule.

** In general, the window for each visit is \pm 7 days unless otherwise noted.

*** Point of care CBC will be run every 2 weeks during Cycle 2. Once a cycle in subsequent cycles (Cycle 3+).

† Study treatment will end upon evidence of disease progression as defined by IWG for AML. Refer to Section 8 for additional details.

‡ Participants will be followed until death. Participants may be contacted by phone, and survival status will be collected and documented

^ JNJ-40346527 (150 mg) is administered PO twice daily.

B For concomitant medications – enter new medications started during the trial through the EOT visit. Record all medications taken for grade 3 and 4 SAEs as defined in Section 9.6.

C Full physical exam at screening visit. Direct physical exam for all other visits. All physical exams will include assessing weight, vital signs, and ECOG performance status. Height will be measured at screening visit only.

D Chest X-ray at screening will be performed within 28 days prior to the first dose of trial treatment. Scans performed as part of routine clinical management are acceptable for use as the screening image if they are of diagnostic quality and performed within 28 days prior to the first dose of trial treatment.

E After Cycle 1, pre-dose lab samples can be collected up to 72 hours prior to the scheduled time point. Hematology and biochemistry tests should be collected pre-dose on Day 1 of every 28 day cycle. Testing for HCV B or C will only take place during screening.

F For women of reproductive potential, a urine pregnancy test should be performed within 14 days prior to first dose of trial treatment. If urine pregnancy results cannot be confirmed as negative, a serum pregnancy test performed by the local study site laboratory will be required. Pregnancy tests (serum and/or urine tests) should be repeated, if required, per institutional guidelines.

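### If follow-up after end of treatment is by phone, censoring event-free survival (EFS) at last examination while counting every death biases 12-month EFS downward

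*Combined protocol and SAP*

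**What the plan says.** Section 8.2.1 defines EFS from study entry to "relapse from PR or CR or CRI, or death from any cause". Progression in someone who never responded is not on that list. For everyone else, "patients not known to have any of these events are censored on the date they were last examined". In the overall survival (OS) row of the same table, "patients not known to have died at last follow-up are censored on the date they were last known to be alive".

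Section 7.6 provides an end-of-treatment visit within 7 days of stopping drug. After that, Section 7.7 says "Participants will be followed every 6 months until death", and a footnote to the Section 7.10 schedule adds: "Participants may be contacted by phone, and survival status will be collected and documented".

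On analysis, Section 10.2.2 says: "Time-to-event analysis (e.g., Kaplan-Meier and cumulative incidence curves) will be used to evaluate event-free and overall survival". Section 10.4 rules out imputation. EFS at 12 months is a secondary objective (2.2) and a secondary endpoint (3.2.2).

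**The concern.** Under the EFS row, deaths and survival come from different sources of information. A death counts on its date, however it is learned of. Being alive and event-free counts only up to the last examination.

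Take two never-responders who both stop drug at month 2, with phone follow-up. One dies at month 10, so is at risk to month 10 and is then an event. The other is known to be alive at month 14, yet is censored at month 2. Which of them leaves the risk set early depends on the outcome, and Kaplan-Meier assumes that it does not.

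For a never-responder, death is the only possible EFS event, so EFS and OS are the same quantity. The two rows can nevertheless give different estimates from the same data, with EFS the lower. At stake is the 12-month EFS estimate in each assay arm.

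**Working it through.** **The plan's own figures.** The plan gives no EFS assumption or EFS power. Its only design figure is the Simon design (7 + 7 per arm, continue on at least 1 of 7, promising at at least 3 of 14; 5% against 30%). It reproduces: type I error 0.0274, power 0.8101, and 14 is the minimax size. EFS plays no part in it.

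**Inputs from the plan.** The two censoring rules and the list of EFS events (8.2.1); 24 months of accrual plus 12 months of minimum follow-up (10.3.1); minimum follow-up of 12 months from last dose (synopsis); 12-month horizon (3.2.2).

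**Assumptions.** Phone-only follow-up; never-responders; exponential survival S(t) = exp(−λt); true 12-month EFS of 10%, 20% or 30%; exponential time to last examination with mean m = 2 or 3 months; uniform accrual.

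**Small example.** Fourteen never-responders stop drug at month 2, ten die between months 2 and 12, and four are alive at month 12. True 12-month EFS is 4/14 = 28.6%. If j of the four die after month 12 but before the cut, they stay at risk and the other 4 − j are censored at month 2. Kaplan-Meier at month 12 is then j/(10 + j):

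| j | 0 | 1 | 2 | 3 | 4 |
|---|---|---|---|---|---|
| KM at 12 months | 0% | 9.1% | 16.7% | 23.1% | 28.6% |

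The bias shrinks as follow-up lengthens.

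**Month-36 cut.** Each participant's cut falls uniformly between months 12 and 36 after entry. The proportion alive at the cut is q = [S(12) − S(36)]/(24λ). Those participants leave the risk set at their last examination, so the proportion at risk at t ≤ 12 is

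Y(t) = S(t) − q[1 − exp(−t/m)],

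and the rule estimates exp{−∫₀¹² λS(t)/Y(t) dt}. The limiting case, with last examination at entry, can be done by hand: [S(12) − q]/(1 − q).

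| True EFS | λ | q | Limiting case | m = 2 | m = 3 | Loss, m = 2-3 |
|---|---|---|---|---|---|---|
| 10% | 0.192 | 0.0215 | 8.0% | 8.1% | 8.2% | about 2 points |
| 20% | 0.134 | 0.0596 | 14.9% | 15.3% | 15.6% | 4-5 points |
| 30% | 0.100 | 0.1134 | 21.0% | 21.8% | 22.4% | about 8 points |

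For 20%: q = (0.200 − 0.008)/(24 × 0.134) = 0.0596, and (0.200 − 0.0596)/(1 − 0.0596) = 0.149.

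**Cut 12 months after last dose.** Taking last dose as last examination, Y(t) = S(t) − [S(12)/(1 + λm)]·[1 − exp(−t(λ + 1/m))]. The same integral gives about 3-4%, 5-7% and 7-10% for true values of 10%, 20% and 30%.

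**With responders included.** In simulated arms of 14 with 15% responding, median time to relapse 6 months, median time to end of treatment 2 months for non-responders and 12-month OS of 20%, mean 12-month EFS was 17.7% with last-known-alive censoring. Under the written rule it was 13.8% (month-36 cut) or 6.9% (12 months after last dose). The written rule was lower in 51% and 84% of arms, and higher in none.

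**If examinations continue.** With a real examination every 6 months in follow-up, the loss was about 0.7 points or less.

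**The case against.** The premise is not certain. Phone contact is permitted, not required. Most of the Section 7.10 grid cannot be read in the text available, and Sections 7.8 and 7.9 mention follow-up visits. A reader might infer that examinations definitely stop at end of treatment; the documents do not establish that. What stands is that no readable passage requires an examination after that visit, so the estimate depends on how sites conduct follow-up.

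A reader might also infer that EFS collapses to near zero. That needs every participant cut at exactly 12 months, as with j = 0 above, whereas the plan's 12 months is a minimum after 24 months of accrual. A drop from 46% to about 32% can also be derived, but the 46% takes the 10% three-year OS ceiling in Section 1.1 through an exponential curve (0.10^(1/3) = 0.464). It is an upper end, not an expected value.

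Nor is everyone who stops drug affected in the same way. Section 4.6 bars contact after consent is withdrawn, so those participants' later deaths are not sought either. Section 7.7 follows toxicity cases until the event resolves or stabilises. Section 6.3 lets participants with stable disease and clinical benefit stay on drug.

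Missed relapses in responders who stop drug push the other way (about 0.3 to 4 points at 5-30% response and 12-month OS of 25%), but the net bias stayed downward in every scenario tried. If progression without response counted as an event, and 70-85% had progressed by last examination, the loss at 20-30% survival would fall to about 1-3 points. The plan does not count it.

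Finally, with 14 participants the sampling standard deviation is about √(0.2 × 0.8/14) = 11 to √(0.3 × 0.7/14) = 12 points, more than the month-36 bias. That limits the practical weight of the point; it does not make the estimator right.

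**Conclusion.** The point holds conditionally: it should be fixed, with moderate confidence. As written, the EFS row makes censoring depend on the outcome whenever follow-up is by phone, and the direction is downward. For never-responders at a month-36 cut the loss is about 2, 4-5 and 8 points at true 12-month EFS of 10%, 20% and 30%. It is larger with a cut 12 months after last dose, and under 1 point with real 6-monthly examinations. The survival and treatment-duration values are assumed; the documents give neither.

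A reader might infer that the trial's conclusions are at risk. They are not: EFS is secondary, with no hypothesis, power or decision rule, and the primary response endpoint, futility rule and safety rule do not use it. OS is censored correctly.

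**What to change.** Amend the EFS row of Section 8.2.1 before any EFS analysis:

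- **Never reached PR or better:** censor at the date last known alive, as in the OS row.
- **Responders, main analysis:** keep every death as an event, and censor those without an event at the last disease assessment.
- **Responders, sensitivity analysis:** censor at the date last known alive and without known relapse.

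Any rule that ignores deaths outside an assessment window would conflict with counting death from any cause. Report such a rule, if at all, as a separate, labelled sensitivity endpoint.

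The cost is a few sentences in Section 8.2.1 and one sensitivity table. Survival status is already collected, so no new data are needed, and the change does no harm if follow-up examinations do take place.
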